5.3. Definition of the variables of study

Main Variables

- Total cholesterol, cLDL , cHDL , triglycerides in mg/ dL . It will be measured at baseline, week 24 and 48.

Secondary Variables

- Number, size and composition of lipoprotein particles by proton magnetic resonance spectroscopy at baseline, week 24 and 48.
- Anthropometric profile (weight, body mass index, abdominal circumference) at baseline, week 24 and 48.
- CD 3,CD 45,CD4,CD8,CCR7,CXCR3,CCR6,CD103,FOXP3,CD25,CD45RA and CD45RO. Quantification in blood in visits basal, 24 weeks and 48 weeks of cells with markers.
- IL-6, TNF-alpha, IFN-gamma, sCD163, sCD14, MADCAM-1, sCD14 and LPS. Quantification in serum in visit basal, 24 weeks and 48 weeks of
- Rigidity arterial extent by the speed of vole of pulse in the visit basal, week 24 and 48.
- Levels of Trimethylamine -N-Oxide serum (TMAO) in the in the visit basal, week 24 and 48.

- Scale MEDAS of adherence to the diet Mediterranean measures in the Baseline visit, week 24 and 48
- Questionnaire of quality of life EQ-5D in the visit basal, week 24 and 48.
- Presence of atheromatous plaque at the coronary level at the baseline visit and at week 48
- Presence of calcium, fibrous and fatty fraction in the coronary plaque at the baseline visit and at week 48
-

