Inclusion-exclusion criteria	
Criteria of inclusion:
 
 - Participant \geq 18 years. - Infection by HIV confirmed by serology. - Treatment antiretroviral asset (TAR). - Burden viral undetectable during to the less 12 months (HE allows a blip below 200 copies). - LDL >140 mg/ dL . - Mediterranean Diet Adherence Screener (MEDAS) less than 9 points (adherence low) for ease the detection of changes after the intervention. 
Criteria of exclusion:
 
 - Participants in treatment lipid-lowering. - Treatment with anti-inflammatory chronic. - Hepatitis B, C or Others conditions inflammatory chronicles active. - Hypercholesterolemia familiar No treated. - Hypothyroidism No controlled. - Impossibility of give he consent.
Treatments or interventions	Advice dietary, analysis blood, measurement of the pulse arterial
Variables	
Cholesterol total, cLDL, cHDL, triglycerides
 
Number, size and composition of particles of lipoproteins
 
Anthropometric profile
 
CD 3, CD45, CD4, CD8, CCR7, CXCR3, CCR6, CD103, FOXP3, CD25, CD45RA and CD45RO
 
IL-6, TNF-alpha, IFN-gamma, sCD163, sCD14, MADCAM-1, sCD14 and LPS.
 
Rigidity arterial extent by the speed of pulse
 
Trimethylamine -N-Oxide
 
Scale MEDAS of adherence to the diet Mediterranean

	Atheroma plaque (number of plaques) Plaque composition (% fibrosis, % calcium, % fat) Coronary calcium index
--	--

	Questionnaire of quality of life EQ- 5D
Population and No. subjects	100 patients of the unit of HIV
Participating centers	Hospital of the Sea. Barcelona
Study Description	Study comparative of the intervention dietetics conventional with a personalized dietary intervention
Overall duration from the study	January 2025- December 2026
Duration of the study for the patient	48 weeks

Board 1. Calendar of the study / procedures for a subject

	Screening (max 28 days before baseline visit)	visit (randomization)	W4 (+/- 7d)	W12 (+/-7d)	W24 (+/-7d)	W48 (+14-7d)
Type of visit	In person	In person			In person	In person
Intervention group			Virtual	Virtual		
Cluster control			No visit	No visit		
Informed consent	x					
Criteria of inclusion and exclusion	x					
Demographic data	x					
History medical	x					
Related story with HIV	x					
Exam physical		x			x	x
Anthropometric data		x			x	x
Questionnaires (MEDAS, FFQ, SMAQ, EQ- 5D and IPAQ)	x (only MEDAS)	x			x	x
Concomitant medication	x	x		x	x	x

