Adverse effects		x		x	x	x
Test of pregnancy		x			x	x

if applicable						
Analytical studies	Valid available last 28 days	x			x	x
Sample storage		x			x	x
Pulse wave velocity		x			x	
Interview with nutritionist		x	x*	x*	x	
Noninvasive coronary artery angiography using CT (CCTA)		x				x

*Only cluster intervention

INDEX

1. List of abbreviations
2. History of versions
3. Frame theorist
 - 3.1. Background and justification of the study
 - 3.2. Hypothesis
4. Goals
5. Methodology
 - 5.1. Design of study
 - 5.2. Study population, inclusion/exclusion criteria and subject withdrawal criteria
 - 5.3. Definition of the variables of study
6. Procedures of the study
7. Period of the study
8. Methods statisticians
9. Aspects ethical
10. Management of samples
11. Confidentiality of the data
12. Literature
13. Annexes

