Objective 1. Evaluate changes in the metabolic and lipid profile:

- Objective 1a. To evaluate changes in the lipid profile (total cholesterol, LDL-C, HDL-C, triglycerides) at week 24 compared to baseline.
- Objective 1b To evaluate the number, size and composition of lipoprotein particles by proton magnetic resonance spectroscopy at week 24 compared to baseline.
- Objective 1c. Percentage of people with increased high-density lipoprotein (HDL) levels >5%.
- Objective 1d. To assess changes in the anthropometric profile (weight, body mass index, abdominal circumference) at week 24 compared to baseline.

Aim 2. Assess changes in he profile inflammatory and of immunoactivation :

- Aim 2a. Assess the changes in the activation immune of the T cell compartment at week 24 compared to baseline.
- Objective 2b. Percentage of patients with reduced inflammatory and bacterial translocation markers at week 24 compared to baseline.

Objective 3. To evaluate changes in arterial stiffness levels measured by pulse wave velocity at week 24 compared to baseline.

Aim 4. Proportion of Participants with decline of >20% of TMAO in the week 24 compared to baseline.

Aim 5. Proportion of Participants with increase of >2 points in the scale MEDAS adherence to the Mediterranean diet at week 24 compared to baseline

Objective 6. Proportion of participants who improve in the quality of life questionnaire. EQ-5D life at week 24.

Objective 7. Evaluate the persistence of all changes included in objectives 1 to 6 at week 48 (24 weeks after the end of the intervention)

Objective 8. To assess the burden of subclinical atherosclerotic coronary disease and changes 1 year after intervention.

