***Cluster Intervention (67 participants):**

The intervention group will receive at the beginning a motivational interview with a personalized portfolio provided by a nutritionist on the Mediterranean diet and adherence to the diet: with information on the food components; desirable frequency of intake; recipes, use of olive oil, walnuts, hazelnuts and almonds. Individual guidelines will be planned individually to improve the lipid profile and improve food choices considering dietary habits, socioeconomic status and nutritional needs (and the score obtained on the MEDAS scale).

At weeks 4 and 12 (virtual), the patient will have a new interview with the nutritionist to review the recommendations, discuss difficulties with diet adherence, design weekly dietary plans and shopping lists. At week 24 and 48, an in-person visit will be held to perform all the procedures of the baseline visit again (including blood draws).

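### Board 1 leaves out the week-48 pulse wave velocity measurement that Section 5.3, Section 6 and Objective 7 require

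*Protocol*

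**What the plan says.** Four parts of the protocol bear on when PWV is measured.

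- **Section 5.3, secondary variables**, gives the measurement times: "Rigidity arterial extent by the speed of vole of pulse in the visit basal, week 24 and 48".
- **Section 4, Objectives.** Objective 3 is "To evaluate changes in arterial stiffness levels measured by pulse wave velocity at week 24 compared to baseline". Objective 7 is to "Evaluate the persistence of all changes included in objectives 1 to 6 at week 48", so it takes in Objective 3. The Summary lists the same persistence goal.
- **Section 6, procedures.** PWV is measured at Visit 1 (baseline). For the intervention arm, "At week 24 and 48, an in-person visit will be held to perform all the procedures of the baseline visit again". The paragraph on the standard-treatment arm likewise says that the baseline measurements are taken again at weeks 24 and 48.
- **Board 1, the calendar of procedures for a subject.** Its columns are screening, baseline (randomization), W4, W12, W24 and W48. The PWV row has two marks, at baseline and at W24: "Pulse wave velocity x x". The W48 cell is empty.

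**The concern.** A visit calendar is a natural working reference at a study visit, and this one disagrees with the text about one of the stated outcomes. Staff who work from Board 1 will not measure PWV at week 48, and the question of whether any change in arterial stiffness lasts beyond the intervention will have no data. Staff who work from Sections 5.3 and 6 will measure it. If practice is mixed, week-48 PWV will be missing for some participants for reasons tied to how the visit was run, which is an awkward pattern in a trial of this size.

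The protocol gives the outcome some weight. Section 3.1 describes arterial stiffness as a dependable marker of cardiovascular damage and PWV as an indicator of aortic stiffness that predicts adverse cardiovascular events. The fifth hypothesis names the pulse wave among the things the diet is expected to change.

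**Working it through.** No power, alpha or event figure is involved, and the protocol states no number to reproduce. The check is a comparison of passages plus a simple count.

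**Step 1. Is the empty cell real or a fault of text extraction?** Other rows in the same part of the table can be read against the same columns. Sample storage, for example, carries three marks, at baseline, W24 and W48: "Sample storage x x x". The coronary CT row is marked at baseline and W48. The PWV row has the same cell layout and ends in an empty last cell. An extraction fault is therefore unlikely.

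**Step 2. PWV time points by source.**

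| Source | Baseline | Week 24 | Week 48 |
|---|---|---|---|
| Section 5.3 | yes | yes | yes |
| Section 6, intervention arm | yes | yes | yes |
| Section 6, standard-treatment arm | yes | yes | yes |
| Objectives 3 and 7 together | yes | yes | yes (implied) |
| Board 1 | yes | yes | **no** |

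**Step 3. Is PWV treated like the other outcomes in Board 1?** The measures that serve Objectives 1 to 6 map to Board 1 rows as follows.

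| Objective | Board 1 row | W48 mark |
|---|---|---|
| 1a, 1c lipids | Analytical studies | yes |
| 1b lipoprotein particles | Sample storage | yes |
| 1d anthropometry | Anthropometric data | yes |
| 2 immune and inflammatory markers | Sample storage | yes |
| 3 arterial stiffness | Pulse wave velocity | **no** |
| 4 TMAO | Sample storage | yes |
| 5 MEDAS, 6 EQ-5D | Questionnaires | yes |

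PWV is the only outcome under Objectives 1 to 6 without a week-48 mark.

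**Step 4. Size.** Planned enrolment is 67 + 33 = 100.

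- Section 5.3: 3 time points × 100 = 300 planned PWV assessments.
- Board 1: 2 time points × 100 = 200.
- Difference: 300 − 200 = 100, which is every week-48 assessment and one third of the PWV assessments planned in Section 5.3.

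These are ceilings, because they ignore dropout and assume the calendar is followed throughout. In that case the number of week-48 values is 0 in each arm, and neither a change from baseline to week 48 nor a between-arm contrast at week 48 can be estimated for PWV.

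**The case against.** The strongest reply is that one blank cell stands against everything else in the protocol, so it is most plausibly a clerical slip and staff may measure PWV anyway. No section says that Board 1 overrides Sections 5.3 and 6. Section 6 is also not fully literal: coronary CT is a baseline procedure in Board 1 but is not marked at week 24, and the nutritionist interview is blank at week 48. A general instruction to repeat the baseline procedures therefore cannot prove by itself that PWV is due at week 48. Finally, PWV is a secondary variable, and its week-24 comparison is fully covered by the calendar.

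Part of this stands. The loss depends on the calendar being followed, the figure of 100 is a worst case, and Section 6 is supporting evidence only. But Section 5.3 sets times variable by variable. It gives the coronary plaque variables baseline and week 48 only, and gives PWV all three times, so the week-48 entry for PWV is specific. No section ranks the text above the calendar either: Section 7 says only that the tests foreseen in the protocol are done at the final visit, which does not settle which source governs. That the slip is probably clerical is a reason to correct it before it affects visits. It does not remove the contradiction.

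**Conclusion.** The contradiction is real and lies within the current text. Board 1 is the outlier: Section 5.3 explicitly requires PWV at week 48, Objective 7 needs it, and Section 6 supports it in both arms.

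Following Board 1 would leave no week-48 PWV data for up to 100 participants, and the Objective 3 component of Objective 7 would be unanswerable. A statistical analysis plan could not repair this, because the measurement would never have been taken.

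The damage is confined to one secondary variable at one time point. Objective 3 itself, the main lipid variables and the other outcomes under Objectives 1 to 6 keep their scheduled assessments. The conclusion assumes that the Board 1 row has been read correctly, which the neighbouring rows support, and that at least some visits are run from the calendar, which the protocol neither states nor excludes. The correction should be made, but it does not threaten the main comparison.

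**What to change.** Mark PWV at W48 in Board 1 for both arms, so that it agrees with Section 5.3, Section 6 and Objective 7.

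If the omission is intended, make the opposite change throughout: delete week 48 from the PWV entry in Section 5.3, exclude Objective 3 from Objective 7 and from the matching Summary goal, and state the exception in Section 6 for both arms.

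The first option costs one table cell on paper. In practice it adds no visit, since week 48 is already in person for both arms and the text already plans the measurement. The protocol names the tonometry equipment without giving its location. At a single centre that measures PWV at baseline and week 24, it is reasonable to assume that it will also be available at week 48.

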6. PROCEDURES OF THE STUDY

- Pre-screening visit (Recruitment): carried out by the regular doctor in the outpatient clinics of the HIV unit at Hospital del Mar. Potential candidates who meet the inclusion criteria will be identified. They will be given an appointment for: Initial visit: informed consent will be signed, blood tests will be performed with blood samples (to achieve objectives 1 to 6). A comprehensive history of clinical history, HIV infection, and drug history will be taken. Randomization will be carried out following randomization tables according to age, gender, and ART. They will be referred to an intervention consultation.
- Visit 1 (baseline) : anthropometric measurements will be taken, scales predetermined in the study (annexes) will be passed and the measurement of the pulse wave velocity (according to methods described later). A dietary approach will then be carried out with a different visit schedule:

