7. PERIOD OF THE STUDY

For can carry to cape all he project it we have divided in different stages:

1. Preparation and validation of the protocol. Patient preselection circuits and diagnostic tests.

January 2025 to February 2025.

This phase will be carried out by the researchers: Design of the patient selection circuit within the HIV unit and promotion of the study among the professionals of the unit focused on the need to address the optimization of the lipid profile of this group of people. We will review the processing of the samples (labeling of the samples, contact with the BioBank service , presentation of the study to the doctors for their knowledge). An anonymous registry of candidate patients will be created.

2. Recruitment of patients

From March 2025 to March 2026. It is estimated that it will take at least one year to recruit the 100 patients.

Recruitment will be carried out at the Infectious Diseases Service of Hospital del Mar (HM). The referent will be [name] [name] (IP). The researchers who will coordinate the recruitment process will be [name]. Patients who meet the inclusion criteria will be referred to a specific consultation created ad hoc to carry out the selection visit. This phase will be carried out interchangeably by [name], [name], [name], [name] or [name] [name]. During this visit, informed consent will be signed, the first sample will be extracted for the complete analysis and general data will be collected: background, history of HIV infection, treatment history and the questionnaires and the participant will be randomized.

3. Follow-up of the patient during 48 weeks. From March 2025 to October 2026.
At this stage, the specific intervention itself will be carried out. Nutritionist researcher [name] together with [name] and [name] [name] from the Endocrinology service will carry out a complete nutritional assessment. Anthropometric measurements and a measurement of the speed of movement will be carried out. of the vibe of pulse. HE will perform follow-up according to it notarized.
4. study visits (March 2025 to October 2026). The final study visit with follow-up at 48 weeks will be carried out in all participants. The tests contemplated in the protocol will be carried out. This stage will be carried out by the equipment of the [name] ([name] together with the [name] and [name] [name]).

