10. CONFIDENTIALITY OF THE DATA

This study will be carried out in accordance with the General Data Protection Regulation 2016/679 and Organic Law 3/2018, of December 5, on the Protection of Personal Data and the Guarantee of Digital Rights.

Patient recruitment will be carried out in the outpatient clinics of the HIV unit at Hospital del Mar. Once the participant signs the informed consent, he or she will be assigned a study number that will correspond to his or her medical record number. This will be saved in an encrypted file with a password to which the IP will have access.

The database that will be created ad hoc for the study will not include any data that would allow the patient to be identified: no date of birth, no phone number, no medical record number. Only the study ID. This database will be in The RedCap environment will only be accessible to the study's researchers.

Study data must be verifiable with the source data, which requires access to all original records, laboratory reports, and subject records. Confidentiality of data and patient identity will be maintained during and after the study is completed . Only the principal investigator and authorized study personnel will have access to these confidential records.

None fact used in he analysis and later divulgation of the results of the study will contain some identifiable reference to patient names.

Once the study is completed, the results will be communicated to the relevant authorities, as appropriate, in accordance with local legislation. The data generated will also be published in conferences and scientific journals.

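### Allocation comes from tables at the recruiting team's own visit in an open trial, with no concealment described, and Section 6 places it before several baseline measurements

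*Protocol*

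**What the plan says.** The Summary describes an open randomised trial at one hospital with 100 participants. Section 6 gives 67 to the intervention and 33 to standard care.

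Three places describe how a participant reaches randomisation.

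- **Section 6.** The first step is "Pre-screening visit (Recruitment): carried out by the regular doctor in the outpatient clinics of the HIV unit at Hospital del Mar". An initial visit follows, with consent, blood tests and history. In the same item: "Randomization will be carried out following randomization tables according to age, gender, and ART". Visit 1 (baseline) is the next item, and anthropometry, the scales and pulse wave velocity are taken there.
- **Section 7, item 2.** "Patients who meet the inclusion criteria will be referred to a specific consultation created ad hoc to carry out the selection visit". Several study researchers run this phase interchangeably. "During this visit, informed consent will be signed, the first sample will be extracted for the complete analysis and general data will be collected"; the list of data continues with "treatment history and the questionnaires and the participant will be randomized".
- **Board 1 (study calendar).** Consent and the inclusion and exclusion criteria are ticked only at screening, up to 28 days before baseline. The next column is labelled as the randomisation visit and holds anthropometry, the questionnaires and pulse wave velocity.

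REDCap appears only in Section 10, as the database: "This database will be in The RedCap environment". No section mentions a list holder, sealed envelopes, a central service or any other means of hiding the next assignment.

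**The concern.** In an open, single-centre trial the team sees every past allocation. If those who approach and consent candidates can also see or deduce the next arm, they can, even without intent, influence who is enrolled and when. Selection at entry of this kind cannot be reliably repaired in the analysis. The safeguard is concealment until the participant is irrevocably in the trial, and the protocol describes none.

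The second issue is the order of steps. Under Section 6 the arm is assigned before the Visit 1 measurements. Objectives 3 and 5 concern change from baseline in pulse wave velocity and MEDAS, Objective 6 improvement in EQ-5D, and Objective 1d anthropometric change. A baseline value taken by staff, or reported by a participant, who already knows the arm can shift the change score.

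**Working it through.** The protocol gives no figure to reproduce here. The check is a comparison of the three descriptions, followed by an illustrative calculation.

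**1. Order of steps**

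| Step | Section 6 | Section 7, item 2 | Board 1 |
|---|---|---|---|
| First identification | Regular doctor, before the initial visit | Candidates referred to the selection visit | Not shown |
| Consent | Initial visit | Selection visit | Screening |
| Randomisation | Initial visit | Selection visit | Baseline visit |
| Scales/questionnaires | Visit 1, after randomisation | Selection visit, listed before randomisation | Baseline visit (only MEDAS also at screening) |
| Anthropometry, pulse wave velocity | Visit 1, after randomisation | Not in item 2; under follow-up in item 3 | Baseline visit, order within the visit not given |

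Sections 6 and 7 agree that consent and randomisation share a visit; Board 1 separates them. Sections 6 and 7 also differ on whether questionnaires precede randomisation. The initial blood sample is listed before randomisation in both sections, so the baseline-measurement point concerns the scales, anthropometry and pulse wave velocity rather than the main lipid variables.

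**2. Allocation ratio.** 67 + 33 = 100 and 67/33 = 2.03, so about 2:1.

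**3. How predictable could allocation be?** Permuted blocks are an assumption; the protocol mentions none. An allocation is certain when all places left in the block belong to one arm. With a places for A and b for B, the expected length of the final single-arm run is a/(b+1) + b/(a+1).

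- Block of 3 (a = 2, b = 1): 2/2 + 1/3 = 1.333; 1.333/3 = 44.4%. Enumeration agrees: AAB, ABA and BAA give 1 + 1 + 2 = 4 certain positions of 9.
- Block of 6 (a = 4, b = 2): 4/3 + 2/5 = 1.733; 1.733/6 = 28.9%. Enumeration: 26 of 90 positions.

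These hold for complete blocks, a known block size and full knowledge of past allocations in the stratum. Stratifying by age, gender and ART leaves incomplete blocks. Simulating 100 participants over 8 to 24 equally likely strata (assumed) gives about 42% falling to 36–37% for blocks of 3, and about 25% falling to 15% for blocks of 6. With simple 2:1 randomisation no allocation is certain.

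**4. Correct guesses of the next arm.** Always guessing the larger arm is right 2/3 = 66.7% of the time. Using known blocks and visible history, simulation with 1 to 12 strata gives 77.6% to 76.5% for blocks of 3, 74.2% to 72.5% for blocks of 6, and 72.6% to 70.3% for blocks of 9. The gain over the ratio alone is therefore about 4 to 11 percentage points (70.3 − 66.7 = 3.6; 77.6 − 66.7 = 10.9). A recruiter who could read the table would be right every time, but no section says that recruiters can.

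**The case against.** The strongest reply is that this is an undescribed safeguard and not a stated error. Both sentences on randomisation are in the passive voice. A stratified table held by someone outside the clinic fits the text as well as one in the consulting room. This stands against three stronger readings that a reader might draw.

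- **That the person who judges eligibility also allocates.** The document does not say so. The regular doctor makes the first identification, and the person who reads the table is not named.
- **That the next allocation is known to recruiters.** No section gives them access. What the text supports is that foreknowledge is not excluded.
- **That consent and randomisation certainly share a visit.** Board 1 says otherwise, so this is one of two conflicting versions.

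It is also fair that most entry criteria are records or laboratory values, and that MEDAS is a scored questionnaire with a fixed cut-off which Board 1 places at screening. The scope for discretion over eligibility is therefore limited; the timing of an approach and the decision to make one remain open. Nor does the document show that every outcome would be biased.

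The reply does not dispose of the point. Who assigns the arm, when, and how it is hidden are matters of conduct that a protocol settles, and an analysis plan cannot restore concealment after enrolment. The protocol does state a method and a place for it, and both are weaker than they need to be in an open trial.

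**Conclusion.** The point holds as a risk that the protocol leaves open, together with an internal contradiction. Sections 6 and 7 put consent and table-based allocation in the recruiting researchers' visit with no concealment described. Section 6 puts allocation ahead of the baseline scales, anthropometry and pulse wave velocity. Board 1 gives a different sequence.

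The document does not allow the bias to be quantified. The 44% and 29% figures are illustrative: they assume 2:1 permuted blocks of 3 or 6, all complete, with block size and history known, and incomplete blocks within strata would reduce them. The change is recommended because it is cheap and removes the doubt; no breach of concealment has been shown.

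**What to change.** - In Section 6, replace the tables with concealed allocation, for example a REDCap randomisation module. Section 10 names REDCap only as the database, so the availability of that function must be confirmed.
- Have someone outside the recruiting team prepare the 2:1 list, stratified by age, gender and ART. If blocks are used, vary their size and keep the sizes out of documents that recruiters see.
- State that the arm is released only after consent, confirmed eligibility and completed baseline measures are recorded, and list which measures count.
- Reconcile Section 6, Section 7 (items 2 and 3) and Board 1, so that consent, eligibility, baseline measurement and randomisation have one order.

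The cost is one independent person to prepare the list, some set-up, and edits in three places. Under Section 6 as it stands, releasing the arm after the baseline measures also moves randomisation from the initial visit to Visit 1, so the change is more than one sentence.
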